7.1.4.2 Evaluation of Non-Target Lesions

Complete Response (CR): Disappearance of all non-target lesions. All lymph nodes should be non-pathological in size (<10 mm short axis)

Non-CR/Non-PD: Persistence of one or more non-target lesion(s)

Progressive Disease (PD): Appearance of one or more new lesions and/or unequivocal progression of existing non-target lesions.

Although a clear progression on non-target lesions in absence of stable target lesions is exceptional, the opinion of the treating physician should prevail in such circumstances.

7.1.4.3 Evaluation of Best Overall Response

The best overall response is the best response recorded from the start of the treatment until disease progression/recurrence (taking as reference for progressive disease the smallest measurements recorded since the treatment started). The patient's best response assignment will depend on the achievement of both measurement and confirmation criteria.

Table 6. Response Evaluation as per RECISTv1.1				
Target Lesions	Non-Target Lesions	New Lesions	Overall Response per RECISTv1.1	Confirmed Response for this Category Requires:
CR	CR	No	CR	>4 wks. confirmation
CR	CR Non-CR/PD	No	PR	≥4 wks. confirmation
PR	CR Non-CR/PD	No		
SD	CR Non-CR/PD	No	SD	Documented at least once ≥4 wks. from baseline
PD	Any	Any	PD	
Any	PD*	Any		
Any	Any	Yes		

* Only in exceptional circumstances, unequivocal progression in non-target lesions may be accepted as disease progression.
 
Note: Patients with a global deterioration of health status requiring discontinuation of treatment without objective evidence of disease progression at that time should be reported as “symptomatic deterioration”. Every effort should be made to document the objective progression even after discontinuation of treatment.
				

NA=not applicable

Note: If subjects respond to treatment and are able to have their disease resected, the patient's response will be assessed prior to the surgery.

7.1.5 Duration of Response

Duration of overall response: The duration of overall response is measured from the time measurement criteria are met for CR or PR (whichever is first recorded) until the first date that recurrent or progressive disease is objectively documented (taking as reference for progressive disease the smallest measurements recorded since the treatment started).

Duration of stable disease: Stable disease is measured from the start of the treatment until the criteria for progression are met, taking as reference the smallest measurements recorded since the treatment started.

7.2 Safety/Tolerability

Analyses will be performed for all patients having received at least one dose of study drug. The study will use the CTCAE version 5.0 for reporting of adverse events (<http://ctep.cancer.gov/reporting/ctc.html>).

8.0 ADVERSE AND OTHER REPORTABLE EVENTS

8.1 Adverse Event Reporting Requirements

Adverse event (AE) monitoring and reporting is a routine part of every clinical trial and is done to ensure the safety of subjects enrolled in the studies as well as those who will enroll in future studies using similar agents. Data on adverse events will be collected from the time of the initial study treatment administration through 100 days after the last dose of study treatment. Any serious adverse event that occurs more than 100 days after the last study treatment and is considered related to the study treatment or intervention must also be reported. Serious Adverse Events (SAEs) will continue to be followed until:

- Resolution or the symptoms or signs that constitute the serious adverse event return to baseline;
- There is satisfactory explanation other than the study treatment for the changes observed; or
- Death.

The investigator is responsible for the detection, documentation, grading and assignment of attribution of events meeting the criteria and definition of an AE or SAE. The definitions of AEs and SAEs are given below. It is the responsibility of the principal investigator to ensure that all staff involved in the trial is familiar with the content of this section.

Any medical condition or laboratory abnormality with an onset date before initial study treatment administration is considered to be pre-existing in nature. Any known pre-existing conditions that are ongoing at time of study entry should be considered medical history.

All events meeting the criteria and definition of an AE or SAE, as defined in Section 8.3, occurring from the initial study treatment administration through 100 days following the last dose of the study treatment must be recorded as an adverse event in the patient's source documents and on the CRF regardless of frequency, severity (grade) or assessed relationship to the study treatment or intervention. However, with regards to laboratory and vital sign abnormalities, only those which require protocol treatment to be modified or treatment to be rendered should be reported as AEs

In addition to new events, any increase in the frequency or severity (i.e., toxicity grade) of a pre-existing condition that occurs after the patient begins study treatment is also considered an adverse event. However, anticipated fluctuations of pre-existing conditions, including the disease under study, that don't represent a clinically significant exacerbation or worsening, need not be reported as AEs.

8.2 Definitions

8.2.1 Adverse Event

An adverse event (AE) is any untoward medical occurrence in a patient receiving study treatment and which does not necessarily have a causal relationship with this treatment. An AE can be any unfavorable and unintended sign (including an

abnormal laboratory finding), symptom, or disease temporally associated with the use of an experimental intervention, whether or not related to the intervention.

- Diagnostic and therapeutic non-invasive and invasive (i.e., surgical) procedures will not be reported as adverse events. However, the medical condition for which the procedure was performed must be reported if it meets the definition of an adverse event unless it is a pre-existing (prior to protocol treatment) condition.

8.2.2 Serious Adverse Event

An adverse event is considered “serious” if, in the view of either the investigator or sponsor-investigator, it results in any of the following outcomes:

- **Death**
If death results from (progression of) the disease, the disease should be reported as event (SAE) itself.
- **A life-threatening adverse event**
An adverse event is considered ‘life-threatening’ if, in the view of either the investigator [or sponsor], its occurrence places the patient or subject at immediate risk of death. It does not include an adverse event that, had it occurred in a more severe form, might have caused death.
- **Inpatient hospitalization or prolongation of existing hospitalization for \geq 24 hours**
- **A persistent or significant incapacity or substantial disruption of the ability to conduct normal life functions**
- **A congenital anomaly/birth defect**
- **Important medical event: Any event that may not result in death, be life-threatening, or require hospitalization may be considered serious when, based upon appropriate medical judgment, they may jeopardize the patient and may require medical or surgical intervention to prevent one of the outcomes listed in this definition of “Serious Adverse Event”.**
Examples of such medical events include allergic bronchospasm requiring intensive treatment in an emergency room or at home; convulsions that do not result in inpatient hospitalization or the development of drug dependency or drug abuse.

Previously planned (prior to signing the informed consent form) surgeries should not be reported as SAEs unless the underlying medical condition has worsened during the course of the study. Preplanned hospitalizations or procedures for preexisting conditions that are already recorded in the patient’s medical history at the time of study enrollment should not be considered SAEs. Hospitalization or prolongation of hospitalization without a precipitating clinical AE (for example, for the administration of study therapy or other protocol-required procedure) should not be considered SAEs. However, if the preexisting condition worsened during the course of the study, it should be reported as an SAE.

8.2.3 Potential Drug Induced Liver Injury (DILI)

Wherever possible, timely confirmation of initial liver-related laboratory abnormalities should occur prior to the reporting of a potential DILI event. All occurrences of potential DILIs, meeting the defined criteria, must be reported as SAEs.

Potential drug induced liver injury is defined as:

1. AT (ALT or AST) elevation > 3 times upper limit of normal (ULN)

-
- AND
2. Total bilirubin > 2 times ULN, without initial findings of cholestasis (elevated serum alkaline phosphatase)
AND
 3. No other immediately apparent possible causes of AT elevation and hyperbilirubinemia, including, but not limited to, viral hepatitis, pre-existing chronic or acute liver disease, or the administration of other drug(s) known to be hepatotoxic.

8.2.4 Expected Adverse Events

An adverse event (AE) is considered “expected” if:

- For approved and marketed drugs or devices, those adverse events are described in the approved Package Insert (Label).
- For investigational new drugs or devices, those adverse events are described in the FDA Investigator’s Brochure.
- In clinical research studies, information on expected adverse events is also summarized in the protocol and in the consent document. See section 9.1.9 for the list of expected adverse events related to the drug under study.

8.2.5 Unexpected Adverse Event

An adverse event (AE) is considered “unexpected” if it is not described in the Package Insert, Investigator’s Brochure, in published medical literature, in the protocol, or in the informed consent document.

8.3 Adverse Event Characteristics

8.3.1 CTCAE Term

(AE description) and grade: The descriptions and grading scales found in the NCI Common Terminology Criteria for Adverse Events (CTCAE) version 5.0 will be utilized for AE reporting. All appropriate treatment areas should have access to a copy of the CTCAE version 5.0. A copy of the CTCAE version 5.0 can be downloaded from the CTEP web site. (<http://ctep.cancer.gov>)

8.3.2 Attribution of the AE

The investigator or co-investigator is responsible for assignment of attribution.

RELATED

Definite – The AE *is clearly related* to the study treatment.

Probable – The AE *is likely related* to the study treatment.

Possible – The AE *may be related* to the study treatment.

UNRELATED

Unlikely – The AE *is doubtfully related* to the study treatment.

Unrelated – The AE *is clearly NOT related* to the study treatment/intervention.

8.4 Serious Adverse Event Reporting Guidelines

8.4.1 Reporting procedures for multi-site trials

All serious adverse events (SAEs) and unanticipated problems (UPs), regardless of causality to study drug, will be reported to the Principal Investigator and also to the Coordinating Center. All SAEs and UPs must be reported to the Coordinating Center within 1 business day of first awareness of the event. Events should be

reported using the Coordinating Center's SAE form as available in the study database. A copy of the SAE form as available in the study database should be sent to the Coordinating Center via fax at [contact] or via email to [contact] within 1 business day of the site's knowledge of the event.

Follow-up information must also be reported within 1 business day of receipt of the information by the investigator.

All SAEs and UPs will be reported to the IRB per current institutional standards.

The Coordinating Center will disseminate information regarding SAEs and UPs to the participating sites within 5 business days of review of the information by the Coordinating Center's Principal Investigator (or designee in the event of extended absence) only in the case that the event(s) is believed to be related (i.e., possibly, probably, or definitely) to the study drug. The Coordinating Center will be responsible for reporting of events to the FDA and supporters, as appropriate (outlined below).

8.4.2 Reporting procedures to Exelixis

All Serious Adverse Events (SAEs) occurring from the initial study treatment administration through 30 days following the last dose of the study treatment will be reported by the Coordinating Center to Exelixis. Any SAEs occurring after 30 days following the last dose of the study treatment that are believed to be related to study drug will also be reported to Exelixis.

The Coordinating Center will send the initial completed SAE Form within 1 business day of receipt via email to [contact] or [contact].

If only limited information is initially available or an ongoing SAE changes in its intensity or relationship to the study drug, or if new information becomes available, a follow-up report will be generated and sent to Exelixis within 1 business day of receipt.

Pregnancy (in subject or partner) or lactation exposure, although not an SAE, should be reported to Exelixis. Forms will be provided to the study sites upon request. The outcome of a pregnancy (for a subject or for the partner of a subject) and the medical condition of any resultant offspring must be reported to Exelixis. Any birth defect or congenital anomaly must be reported as an SAE, and any other untoward events occurring during the pregnancy must be reported as AEs or SAEs, as appropriate.

8.5 Routine Reporting

All other adverse events- such as those that are expected, or are unlikely or definitely not related to the study participation- are to be reported annually as part of regular data submission.

8.6 Reporting of Pregnancy

Pregnancies that occur during study participation or within 6 months of last study dose should be reported to the Coordinating Center via e-mail at [contact] immediately upon site's knowledge of the event.

8.7 Reporting of Unanticipated Problems

There are types of incidents, experiences and outcomes that occur during the conduct of human subjects research that represent unanticipated problems but are not considered

adverse events. For example, some unanticipated problems involve social or economic harm instead of the physical or psychological harm associated with adverse events. In other cases, unanticipated problems place subjects or others at increased risk of harm, but no harm occurs.

Upon becoming aware of any incident, experience, or outcome (not related to an adverse event) that may represent an unanticipated problem, the investigator should assess whether the incident, experience, or outcome represents an unanticipated problem. The incident, experience or outcomes is considered unanticipated if it meets all of the following criteria:

1. Unexpected (in terms of nature, severity, or frequency);
2. Related or possibly related to participation in the research; and
3. Suggests that the research places subjects or others at a greater risk of harm than was previously known or recognized.

If the investigator determines that the incident, experience, or outcome represents an unanticipated problem, the investigator must report it to the IRB within 14 calendar days of the study team becoming aware of the problem.

8.8 Safety Report Reconciliation

The Sponsor will reconcile the clinical database SAE reports transmitted to Exelixis. Frequency of reconciliation should be every 3 months and prior to the database lock or final data summary. Exelixis will email, upon request from the Investigator, the reconciliation report. Requests for reconciliation should be sent via email. The data elements listed on the reconciliation report will be used for identification purposes.

8.9 Stopping Rules

The DSMC comprised of the principal investigators, co-investigators at University of Michigan, study statistician, and multi-site coordinator will be responsible for the continuous monitoring of the study for treatment tolerability and efficacy. During the monthly meetings current study data will be reviewed and the decision to continue, hold, or stop accrual to this study will be formally considered.

9.0 DRUG INFORMATION

9.1 Cabozantinib

9.1.1 Other Names
Cabometyx®

9.1.2 Classification
Tyrosine kinase inhibitor/Antineoplastic agent

9.1.3 Mechanism of Action
Inhibition of the tyrosine kinase activity of MET, VEGFR-1, -2 and -3, AXL, RET, ROS1, TYRO3, MER, KIT, TRKB, FLT-3, and TIE-2.

9.1.4 Pharmacokinetics

1. Distribution: The oral volume of distribution (V_z/F) of cabozantinib is approximately 319 L. Cabozantinib is highly protein bound in human plasma ($\geq 99.7\%$).

-
2. Elimination: The predicted terminal half-life is approximately 99 hours and the clearance (CL/F) at steady state is estimated to be 2.2 L/hr.

9.1.5 Storage, Preparation and Stability

Cabozantinib can be stored at 20°C to 25°C (68°F to 77°F); excursions are permitted from 15°C to 30°C (59°F to 86°F).

9.1.6 Dose and Administration

1. Dosage: See Section 5.1
2. Administration: Cabozantinib must be taken on an empty stomach. Subjects must be instructed not to eat for at least 2 hours before and at least 1 hour after taking cabozantinib. Subjects should be instructed to take their cabozantinib dose at approximately the same time every day. If a subject misses a dose, the dose may be taken later only if it is within 12 hours of when the missed dose should have been taken. The missed dose should not be made up if it is within 12 hours of the next scheduled dose.

Cabozantinib tablets should be swallowed whole with at least 8 ounces of water. The tablets should not be crushed. Grapefruit, grapefruit juice, Seville oranges and their products should be avoided by subjects taking cabozantinib.

9.1.7 Availability

Cabozantinib tablets are supplied as film coated tablets containing cabozantinib malate equivalent to 20 mg and 60 mg of cabozantinib and contain microcrystalline cellulose, lactose anhydrous, hydroxypropyl cellulose, croscarmellose sodium, colloidal silicon dioxide, magnesium stearate and Opadry® yellow.

60 mg tablets are yellow film-coated, *ova* shaped with no score, debossed with “XL” on one side and “60” on the other side of the tablet; available in bottles of 30 tablets: NDC 42388-023-26

20 mg tablets are yellow film-coated, *round* shaped with no score, debossed with “XL” on one side and “20” on the other side of the tablet; available in bottles of 30 tablets: NDC 42388-024-26

Doses of 40 mg will comprise of two 20-mg tablets.

9.1.8 Handling and Disposal

Cabozantinib disposal should occur in accordance with recommendation from the Food and Drug Administration. (<https://www.fda.gov/drugs/safe-disposal-medicines/disposal-unused-medicines-what-you-should-know>)

9.1.9 Adverse Effects

1. Adverse Effects: Adverse reactions occurring in $\geq 20\%$ of cabozantinib-treated patients in the CELESTIAL clinical trial in patients with HCC, in order of decreasing frequency were: diarrhea, decreased appetite, palmar-plantar erythrodysesthesia (PPES), fatigue, nausea, hypertension, and vomiting (Abou-Alfa, Meyer et al. 2018). Grade 3-4 adverse reactions which occurred in $\geq 5\%$ of patients were PPES, hypertension, fatigue, diarrhea, asthenia, and decreased appetite. There were 6 adverse reactions leading to death in patients receiving cabozantinib (hepatic failure, hepatorenal syndrome, esophagobronchial fistula, portal vein thrombosis, pulmonary embolism,

upper gastrointestinal hemorrhage). Other described AEs include GI fistulas and perforation (1%), thrombotic events (7%), jaw osteonecrosis (<1%), wound complications in the perioperative period, and Reversible Posterior Leukoencephalopathy Syndrome.

For a full description of the safety profile of cabozantinib across multiple cancers, refer to the Cabozantinib Investigator's Brochure.

Adverse events may occur within the first few weeks in the course of treatment with cabozantinib, as cabozantinib is expected to reach steady state exposure at approximately 2 weeks following first dose. Events that generally have an early onset include hypocalcemia, hypokalemia, thrombocytopenia, hypertension, PPES, abdominal pain, mucosal inflammation, constipation, diarrhea, and vomiting.

2. Pregnancy and Lactation: Category D. Based on animal data cabozantinib can cause fetal harm when administered to a pregnant woman.
3. Drug Interactions:
 - Strong CYP3A4 Inhibitors:** Coadministration of a cabozantinib capsule formulation with a strong CYP3A4 inhibitor increased the exposure of cabozantinib, which may increase the risk of exposure-related adverse reactions. Avoid coadministration of cabozantinib with strong CYP3A4 inhibitors. Reduce the dosage of cabozantinib if coadministration with strong CYP3A4 inhibitors. Reduce the dosage of CABOMETYX if coadministration with strong CYP3A4 inhibitors cannot be avoided. Avoidance of grapefruit or grapefruit juice is recommended due to the potential for increased exposure of cabozantinib.
 - Strong CYP3A4 Inducers:** Coadministration of a cabozantinib capsule formulation with a strong CYP3A4 inducer decreased the exposure of cabozantinib, which may reduce efficacy. Avoid coadministration of cabozantinib with strong CYP3A4 inducers. Increase the dosage of cabozantinib if coadministration with strong CYP3A4 inducers cannot be avoided. Avoidance of St. John's Wort is recommended which may lead to decreased exposure of cabozantinib.

10.0 CORRELATIVES/TRANSLATIONAL STUDIES

We will aim to study the HCC tumor microenvironment through the use of pre-treatment tissue collection (mandatory, if available, at all sites) as well as post-treatment tissue collection (optional for patients enrolled at all sites). Identification of important biologic subsets of HCC patients that may have clinical efficacy from cabozantinib will be the overarching goal of this translational science. Tissue (previously collected via core biopsy, surgical excision) may be examined by whole exome analysis, RNA seq and histologically by immunohistochemistry (IHC). Biologic markers and RNA expression will be examined in the context of patient efficacy.

10.1 Pharmacokinetic Analysis

The pharmacokinetic blood draws occur prior (pre-dose) to Cycle 1 Day 15, Cycle 2 Day 1, Cycle 2 Day 15 and Cycle 3 Day 1. See lab manual for details.

10.2 Tissue Collection

Tissue will be collected at the time points specified in section 6.2 Study Calendar. Please refer to the lab manual for sample collection and processing details.

10.3 Blood Collection

Blood samples will be collected at the time points specified in section 6.2 Study Calendar. Please refer to the lab manual for sample collection and processing details.

10.4 Centralized Imaging

All CT scans will be coded using trial patient and site IDs and shipped or electronically uploaded for banking and exploratory endpoint assessment. Please see the lab manual for details regarding shipping address and/or information for electronic upload.

10.5 Specimen Banking

Patient samples collected for this study will be retained at University of Michigan. Specimens will be stored indefinitely or until they are used up. If future use is denied or withdrawn by the patient, best efforts will be made to stop any additional studies and to destroy the specimens.

Specimens being stored long-term for potential use not outlined in the protocol are subject to University Policy Governing Tissue Sample Collection, Ownership, Usage, and Disposition within all UMMS Research Repositories.

11.0 STATISTICAL CONSIDERATIONS

11.1 Study Design/Study Endpoints

This protocol will enroll patients with unresectable or metastatic HCC to cabozantinib in a Phase 1b/2 study design. The trial will be monitored using the Time-To-Event modification of the Continual Reassessment Method (TITE-CRM) (Cheung and Chappell 2000) (O'Quigley, Pepe et al. 1990). This method assumes a model for the time to occurrence of toxic responses as a function of the dose. The time-to-event modification allows information from all patients enrolled and treated (even those with only partial observation) to contribute information for calculating the dose-toxicity relationship. This method is flexible with regard to the number of patients treated at each dose level, patients may be continuously recruited throughout the trial, without recruitment pauses, as long as patients are assigned a dose deemed safe at the time of enrollment.

The primary endpoint is the occurrence/lack thereof of dose-limiting toxicity (defined in Section 5.1.2) during the first 29-days of therapy to identify the maximum tolerated dose/recommended Phase 2 dose (RP2D) in this patient population.

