5.0 TREATMENT PLAN

5.1 Treatment Dosage and Administration

Protocol treatment must start within 14 calendar days of enrollment otherwise the patient will be taken off study. Re-screening is allowed.

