5.1.2 Dose Limiting Toxicities

A DLT will be any of the following occurring during the first 29 days of therapy, attributed (possibly, probably, or definitely) to the drug following day 1 treatment as assessed per the NCI CTCAE v5.0.

1. Grade 4 or greater hematological toxicity with the exception of uncomplicated grade 4 leukopenia/ neutropenia lasting <7 days)
2. Grade 3 or higher thrombocytopenia with bleeding
3. Grade 3 or greater febrile neutropenia.
4. Grade 3 or greater non-hematological toxicity, except nausea, vomiting, diarrhea (exception only when lasting <3 days, or without supportive care measures, such as anti-diarrheal medications), hyperbilirubinemia (secondary to biliary obstruction), alopecia, fatigue, and hypersensitivity reaction
5. Any death not clearly due to the underlying disease or extraneous causes.
6. Grade 3 or higher electrolyte abnormality that lasts >72 hours, or is clinically complicated, or does not resolve spontaneously or with conventional medical interventions.

Any dose modifications deemed necessary for patient safety during this period by the treating investigator would constitute a DLT for that patient – even if not meeting the explicit DLT definition as reported in Section 5.1.2. With completion of cycle 1, and following DLT determination (**yes vs. no**) on cycle 2 day 1, cycle 2 may begin.

Information on dose limiting toxicity events must be entered within one business day, recorded locally and entered into Case Report Forms (CRFs) on the web-based electronic data capture (EDC) system of the University of Michigan.

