5.9 Patient Replacement

All patients who receive at least one dose of study therapy will be considered evaluable for primary endpoint and safety/toxicity.

Patients enrolled in the study will be considered non-evaluable for efficacy under the following case scenarios and replaced by additional patients:

1. Patients who received no investigational therapy.
2. Patients meeting off study criteria 5.8.1 and 5.8.2. As this trial assigns the dose level based upon real-time assessment of the experience of those treated on trial, any partial data from a patient stopping trial therapy early while still within the observation period for dose-limiting toxicity due to criteria 5.8.1 and 5.8.2, will continue to have their partial data used for dose assignments for future patients. However, this type of patient, stopping treatment due to 5.8.1 and 5.8.2 would be replaced to reach the trial's total sample size.

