6.2 Time and Events Table/Schedule of Events/Study Calendar

Table 5. Study Calendar							
Procedures	Screening ¹	Cycle 1		Cycle X		EOT Visit ⁸	Follow-Up Q3 months +/- 1 week ⁹
		Day 1	Day 15	Day 1	Day 15		
Informed Consent	X						
History, Physical Examination	X	X		X		X	
Weight, BSA	X	X		X		X	
Vital Signs	X	X	X	X		X	
Performance Status	X	X		X		X	
Toxicity Evaluations		X	X	X			
Scans with Tumor Measurements	X			X ⁵			
CBC with differential	X	X	X	X			
CMP ²	X	X	X	X			
AFP		X		X ¹⁰		X	
PT/INR, PTT	X						
Pregnancy Test ³	X						
UPCR ¹¹		X		X			
TSH, Free T4 and T3		X		X			
Concomitant Medication Review	X	X		X			
12 lead ECG	X						
PK Blood ¹²			X	X ¹²	X ¹²		
Research Blood ⁴		X		X		X	
Tissue ⁶	X						X
Study Drug Administration ⁷		X	X	X			
Survival Follow-up							X

1. All screening procedures to be completed within 2 weeks of enrollment, except imaging which should be ≤ 4 weeks. Protocol treatment is to begin ≤14 days of enrollment.

-
2. Comprehensive metabolic panel includes BUN/creatinine, sodium, potassium, chloride, glucose, calcium, alkaline phosphatase, AST, ALT, total bilirubin and total protein.
 3. Required for females of childbearing potential. Serum or urine pregnancy test per site investigator discretion.
 4. Cycle 1 Day 1 specimens will be collected prior to administration of initial dose, and Cycle X Day 1 specimens will be collected on Cycle 4 Day 1. Refer to the lab manual for sample collection and processing details.
 5. MRI or CT (abdomen/pelvis) with contrast along with CT chest with/without contrast will be assessed every 8 ± 1 weeks starting from C1D1. Imaging assessment of scans at the site should be completed by either a radiologist or an imaging core, and not by the oncologist nor via abstraction of data from the subjective/clinical radiology report.
 6. Pre-treatment, diagnostic pathology specimens obtained in the course of standard biopsy or surgery, if available. Procurement of tissue is mandatory for enrollment, if available. If tissue from initial biopsy is not available, a repeat biopsy is NOT required and patient will be eligible for enrollment. Post-treatment tissue collection, if available. Refer to the lab manual for sample collection and processing details.
 7. See Section 5.1 for details. Study drug administration with associated labs will have a window of ± 3 days.
 8. End of treatment (EOT) visit should be completed within 30 days of last treatment.

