11.3 Dose Allocation

The dose level for each patient treated on this trial will be determined by the study statistician based upon selecting the dose level with the highest estimated probability of dose-limiting toxicity not to exceed or threshold of 35%, based upon our prior expectation and accumulating trial data; subject to the following constraints:

- The 1st and 2nd patients will be assigned to receive dose level 1
- Intra-subject dose escalation is not permitted
- The dose may be escalated only 1 dose level between adjacently accrued and treated patients. Dose de-escalated between adjacently accrued and treated patients is not restricted.
- At a minimum two patients at a given dose level are required to be completely observed for the DLT observation period (Cycle 1, days 1-28, D1C2 (day 29)) before escalation is allowed.
- Patients will be recruited as available and assigned to treatment according to the TiTE-CRM algorithm. No formal cohort sizes or accrual rate limits are required.

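### The assigned dose is judged safe at enrollment, first dose may follow up to 14 days later, and no step re-reads the TITE-CRM estimate in between

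*Combined protocol and SAP*

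**What the plan says.** - **When the dose is judged safe.** Section 11.1, and the same wording in the synopsis (Statistical Methodology), permits continuous recruitment "as long as patients are assigned a dose deemed safe at the time of enrollment". Enrollment is the only time point attached to the dose decision anywhere in the documents.
- **When treatment starts.** Section 5.1: "Protocol treatment must start within 14 calendar days of enrollment otherwise the patient will be taken off study". Footnote 1 of the study calendar (section 6.2) agrees: "Protocol treatment is to begin ≤14 days of enrollment".
- **How the level is chosen.** Section 11.3 has the statistician take the level with the "highest estimated probability of dose-limiting toxicity not to exceed or threshold of 35" per cent, "based upon our prior expectation and accumulating trial data". It adds: "Dose de-escalated between adjacently accrued and treated patients is not restricted". Section 5.9 states that "this trial assigns the dose level based upon real-time assessment of the experience of those treated on trial". Neither section gives a data cut relative to day 1.
- **How fast DLTs arrive.** Section 5.1.2: "Information on dose limiting toxicity events must be entered within one business day".
- **What the enrollment procedure contains.** Section 4.0 describes an e-mail giving a study identification number and a randomization number. It mentions neither a dose level nor the statistician.
- **What happens after day 1.** Sections 5.1.2 and 5.2 count any dose change made for safety during the DLT period as a DLT, and section 5.2 otherwise bars dose modification in cycle 1.

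**The concern.** TITE-CRM is used so that partial follow-up informs each assignment as it accrues. Here up to two weeks of that follow-up can build up between the stated decision point and the first tablet. A DLT reported in the gap can move the estimate for the assigned level from below 35% to above it, and no step carries that news to the waiting patient.

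The timing matters because first dose is the last clean moment for an update. Once cycle 1 has begun, a change of dose made for safety is scored as a DLT even if the DLT definition is not met, so correcting an out-of-date assignment then could enter the primary endpoint as a toxicity. Section 11.2 also claims that the design protects patients when toxicity is higher than expected, and that is where the gap has most effect.

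There is a second ambiguity. The escalation rule in section 11.3 refers to patients adjacent in accrual and treatment. With gaps of 0 to 14 days the two orders can differ.

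**Working it through.** **Timing.** Maximum gap 14 days (5.1, 6.2); DLT window 29 days (11.1). 14/29 = 0.48. Accrual has no pauses (11.1) and no rate limit (11.3), so DLT windows of earlier patients can overlap the gap.

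**Is there a re-check?** Sections 4.0, 5.1, 5.9, 6.2, 11.1 and 11.3, read side by side, contain none. Sections 5.9 and 11.3 describe ongoing use of the data but set no later cut than enrollment.

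**Accrual.** No rate is given. The schema gives 32 patients and a 3-year study duration. 32/36 = 0.9 per month; over 24 months, 32/24 = 1.3 per month. If accrual were confined to 12 months it would be 32/12 = 2.7 per month.

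**Size, by simulation.** The plan gives no figure on this point. From the documents: prior 20/27/35%, Table 7 Scenario 1 (20/27/35%) and Scenario 2 (20/35/50%), 32 patients, first two at level 1, one-level escalation, two patients fully observed before escalation, 35% limit. Assumed: one-parameter power model, linear weights over 29 days, prior SD 0.3 to 0.6, uniform DLT times, stop if level 0 exceeds 35%, every patient waiting the full 14 days, 400 trials per setting. A patient is flagged if the level assigned at enrollment has an estimate above 35% at first dose.

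| Patients per month | Scenario 1 | Scenario 2 |
|---|---|---|
| 1 | 2.5-4.5% | 3.5-7.1% |
| 2 | 4.0-7.6% | 6.0-11.1% |
| 4 | 5.8-10.5% | 8.6-15.2% |

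At least one patient is flagged in 46-95% of these trials. With a 7-day gap the share of patients is about 1.4-10%.

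Other choices of the unstated inputs, at 1 to 3 patients per month, give about 2-10% with gaps uniform over 0-14 days and about 4-21% with a 14-day gap. At about 1 per month the figures are 2-4% and 4-9%. One such set, with prior SD from 0.3 to 1.16, gave 1.3-10.2% and 2.8-17.7%, so the ends of the ranges are soft.

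**From flags to DLTs.** Approximate excess = share flagged × patients treated × difference in true DLT risk for a one-level move (0.15 in Scenario 2; 0.07 or 0.08 in Scenario 1). With a 14-day gap and 1 patient per month:
- Scenario 1, prior SD 0.3: 0.025 × 31.9 × 0.08 = 0.06.
- Scenario 2, prior SD 0.3: 0.035 × 31.6 × 0.15 = 0.17.
- Scenario 2, prior SD 0.6: 0.071 × 22.7 × 0.15 = 0.24.

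Direct counts over 1 to 3 patients per month give about 0.03-0.42 per trial. The shares must not be multiplied by 32, because trials with a wide prior often stop early under the assumed rule. In Scenario 2 with prior SD 1.16, 71% stopped and 12.5 patients were treated on average.

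**Table 7.** It cannot calibrate these runs. Model form, prior variance, stopping rule and accrual are not given, and no variant tried (power or logistic, prior SD 0.3 to 1.16) matched all its rows. That is not evidence that Table 7 is wrong, and this point does not rest on it.

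**The case against.** The strongest reply is that the sentence in section 11.1 explains why TITE-CRM needs no recruitment pauses and is not the allocation procedure. The operative rule is in section 11.3, which has no time point, and section 5.9 calls the assignment real-time. The enrollment e-mail in section 4.0 does not list a dose. A statistician following these sections could update the level before day 1 without breaching anything. This stands as far as it goes. A reader might infer that the dose is locked at enrollment, but the documents do not say so. What remains is that nothing requires an update, the only stated time point is enrollment, and up to four sites need one written rule.

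A reader might also infer that these patients start at a level already ruled out. That is too strong, because the estimate moves both ways. In simulations with prior SD 0.4 and 1.16, 1 and 3 patients per month and no stopping, the final selected level was at or above the flagged level for 34-64% of flagged patients. Upward changes over the gap were about as common as downward ones (1.8-10% against 1.7-11%). In Scenario 1 no true rate exceeds 35%, so a flag there is estimation noise; in Scenario 2 only level 2 exceeds it.

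Finally, 14 days is a deadline and not an expected wait, and the 3-year duration suggests about 1 patient per month. Both point to the lower part of the ranges. The chance of at least one flagged patient per trial sounds large beside an expected excess well under one DLT.

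**Conclusion.** The gap is real and rests on the text: the only stated decision point is enrollment, first dose may be 14 days later, and no re-reading of the model is required between them. Following the plan as written, a patient may start at a level whose current estimate is above the plan's own 35% limit.

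The effect is small. About 1 patient per month is the more plausible rate, with roughly 2-4% of patients affected if gaps are spread over 0-14 days and 4-9% if all wait the maximum. The expected excess stays well under one DLT per trial at every rate from 1 to 3 per month. These figures depend on accrual, prior variance, stopping rule and actual gaps, none of which the documents give. The finding does not show a locked dose or substantial harm, and it does not undermine the design. It is worth correcting because it touches patient safety, the data are already in hand, and the change is cheap.

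**What to change.** Reconcile the synopsis and sections 4.0, 5.1, 11.1 and 11.3 so that the data cut governing the assigned level is tied to first dose rather than to enrollment:

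- The statistician re-runs or confirms the TITE-CRM shortly before C1D1, using all DLT data entered by then, and applies the existing section 11.3 criterion and constraints.
- Section 4.0 states how the result reaches the site.
- Section 11.3 states whether adjacency in the escalation rule follows order of enrollment or order of first dose.

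Which level a patient then receives is for the sponsor to decide; no dosing rule is proposed here.

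The cost is a few sentences of text, one more model run and site message for each delayed start, and possibly a supply of more than one level kept available until C1D1.
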